6.2 Demographics and Medical History

Subject demographic data such as age, sex, ethnicity (where legally allowed), and race will be obtained during Screening.

The subject's clinically significant and relevant medical history will be obtained at Screening. The medical history should include (but not be limited to) clinically significant and relevant medical history with following body systems: head, eyes, ears, nose, and throat (HEENT), neurologic and psychiatric, endocrine and metabolic, dermatological, cardiovascular, respiratory, gastrointestinal, genitourinary, musculoskeletal, hematologic, lymphatic, hepatic and renal,

immunological, and surgical history. Medical history data will be reviewed and updated, as appropriate, at Day 1.

6.3 Efficacy Assessments

6.3.1 Tumor Imaging and Response

Subjects will have imaging performed at the time points stipulated in the schedule of events ([Table 1](#) and [Table 2](#)).

For individual subjects, the same imaging method should be used for all subsequent image collections throughout the study. The preferred method of imaging is via CT scan with intravenous (IV) contrast (MRI may also be considered as indicated). The slice thickness of images obtained at Pre-screening (i.e., after treatment with first-line systemic anti-cancer therapy), Screening, or while on study must be the same size or smaller than the slice thickness of the image obtained prior to administration of the first dose of first-line systemic anti-cancer therapy used to document all lesions present during staging of the synovial sarcoma. All images must include windows of the chest, abdomen, and pelvis. Brain images will be obtained if symptoms or signs suggest central nervous system involvement. Bone images will be obtained if symptoms, signs, or history suggest bone involvement by metastatic disease.

All images will be evaluated by the investigator using RECIST v1.1 measurement criteria expressed as PR, CR, SD, or PD (see [Appendix 1](#)).

Radiographic images (e.g., CT scan or MRI) will also be submitted to an IRC for storage and will be available for evaluation by a central reader, if requested by the sponsor. Subjects who have a tumor response of SD with evidence of $\geq 15\%$ to 20% increase in tumor burden will be submitted for evaluation by a central reader for adjudication.

The Radiology manual includes complete details for the collection, storage, and evaluation of images.

6.3.1.1 Imaging at Pre-screening

For subjects to be eligible for study participation, the investigator must confirm no evidence of disease progression while the subject is receiving treatment with first-line systemic anti-cancer therapy for unresectable locally-advanced or metastatic disease. During the Pre-screening period, imaging will be performed per standard-of-care and all target and non-target lesions documented before initiating first-line systemic anti-cancer therapy using RECIST v1.1. The images obtained during Pre-screening will be compared with images obtained before the start of first-line systemic anti-cancer therapy, which should have been obtained no more than 60 days prior to administration of the first dose of first-line systemic anti-cancer therapy. For a subject who has no digital images available but has a documented response classification per RECIST v1.1, a radiologist's report certifying no disease progression may be used in individual cases after prior approval by the sponsor.

6.3.1.2 Imaging at Screening

During the Screening period, and before randomization, imaging (images will include all organ systems that had disease present prior to start of first-line systemic anti-cancer therapy) will be performed, and all target and non-target lesions that were documented during Pre-screening will be assessed by the investigator using RECIST v1.1 to determine the subject's response to first-line systemic anti-cancer therapy. The images obtained at Screening will be compared with both images obtained at Pre-screening and images obtained before the start of first-line systemic anti-cancer therapy to ensure that no disease progression has occurred. Subjects who have a tumor response of SD with evidence of $\geq 15\%$ to 20% increase in tumor burden will be submitted for central review to adjudicate the investigator's assessment of tumor response prior to randomization. For individual subjects, the images obtained during the Screening period must have been collected using the same imaging method used for all images. Radiographic images at Screening (e.g., CT scan or MRI) will also be submitted to an IRC for storage and will be available for evaluation by a central reader, if requested by the sponsor. Details for the collection and evaluation of radiographic images are included in the Radiology Manual.

6.3.1.3 Imaging During Treatment to the Time of Disease Progression

Tumor imaging assessments will be performed and evaluated every 8 weeks after Day 1 until investigator-determined PD (using RECIST v1.1) is documented. Disease progression will be assessed by the investigator using RECIST v1.1. For each subject, the images obtained during the Treatment period must have been collected using the same imaging method for all images during the Pre-screening and Screening periods. Subjects who have a global deterioration of health status that is attributed to progressive disease and leads to discontinuation of study treatment, but who are unable to provide radiographic evidence of disease progression (symptomatic deterioration), will be considered as having PD at the time of documented global deterioration of health for the purpose of determining PFS. Radiographic images (e.g., CT scan or MRI) will also be submitted to an IRC for storage and will be available for evaluation by a central reader, if requested by the sponsor. Details for the collection and evaluation of radiographic images are included in the Radiology Manual.

6.3.2 Immune Response Assessments

Results for anti-NY-ESO-1 plasma antibody must be available for subject stratification at the time of randomization. In addition, at select US sites, pre- and post-treatment anti-NY-ESO-1 plasma antibodies may be used for exploratory analyses.

Pre- and post-treatment blood and tumor samples will be collected for exploratory analyses of potential biomarkers of CMB305 immunogenicity and clinical tumor response as shown in [Table 3](#).

Circulating tumor genomics will be collected for exploratory analyses of potential immune response effect on tumor growth.

Table 3 At Select US Sites Only: Immune Response Assessments

Assessment	Subjects/Timepoint	Analysis
Presence of T cell immunity at baseline (peripheral blood)	Day 1 prior to dosing	NY-ESO-1-specific T cells are detected in PBMC by ELISPOT (ex vivo or following 7-day in vitro stimulation). The assay is performed in quadruplicate. Positive response is defined as follows: 
 • ex vivo ELISPOT: no less than 15 IFNγ-secreting spots per well after background subtraction • in vitro stimulation ELISPOT: no less than 50 spots per well after background subtraction
Presence of antibody at baseline (peripheral blood)	Screening	NY-ESO-1 specific plasma antibodies that are detected by ELISA at a titer of $\geq 1:100$
Induction of antibody on treatment (peripheral blood)	Day 92	
 • NY-ESO-1 specific plasma antibodies that are detected by ELISA at a ≥ 4-fold increase in titer at Day 92 or 
 • Seroconversion of NY-ESO-1 specific plasma antibodies that are detected by ELISA at 92
Induction of T cells on treatment (peripheral blood)	Day 92 and only Day 365 for subjects who have not yet progressed	
 • Ratio of post-treatment to pre-treatment NY-ESO-1-specific T cell counts ≥ 2 or 
 • Post-treatment positive ELISPOT from pre-treatment negative baseline
Intratumoral immune status at baseline and on treatment (tumor biopsy)	Fresh biopsy either at Prescreening or Screening, Day 92, Day 365, and at time of progression event will be encouraged	Ratio of post-treatment to pre-treatment NY-ESO-1-specific T cells within the tumor

ELISA = enzyme-linked immunosorbent assay; ELISPOT = enzyme-linked immunospot;

NY-ESO-1 = New York esophageal squamous cell carcinoma-1; PBMC = peripheral blood mononuclear cells

Many exploratory analyses for potential biomarkers are being investigated, but the predictive value of such tests is not yet known. The data collected from these exploratory tests will help to define a set of biomarkers that might be used in future studies to help define the ability of CMB305 to stimulate anti-tumor immune responses and to help stratify subjects who might respond to these treatments. Exploratory blood tests may include functional assays of cytolytic T cells or other immune cells directed against autologous tumor cells or surrogate target cells,

modifications of current assays to detect anti-tumor cellular immunity, detection and/or analyses of circulating tumor cells, or analyses of other (not yet undefined) tumor markers and immune function. Screening and post-treatment cancer biopsy tissue may be collected at select study sites and only if tumor sites are accessible. These tumor samples will be examined for evidence of anti-tumor cellular immunity (e.g., CD8 T cell or natural killer cell infiltration, tumor necrosis) by IHC and for evidence of immune suppression within the tumor microenvironment. Samples may also be sent for gene expression analysis, T cell receptor expression, fluorescence-activated cell sorting analysis, and isolation of tumor-infiltrating lymphocytes. Any blood or tumor samples will only be used to examine the subject's immune response, their cancer, or to help evaluate any potential toxicity arising in the study. The samples will not be examined for unrelated research or to examine unrelated genes or diseases.

The following immune monitoring may be conducted:

- Cellular immunogenicity by changes from baseline and over the course of the trial period in peripheral blood levels of NY-ESO-1 antigen specific T cells and T cell associated cytokine production
- Cellular immunogenicity by changes from baseline and over the course of the trial period in peripheral blood levels of overall T cell effector and memory populations
- Humoral immunogenicity as measured by changes from baseline and over the course of the trial period with anti-NY-ESO-1 antibodies and anti-LV antibodies

Details for sample handling and assay performance will be provided in the Laboratory Manual provided to study sites.

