7.9 Exploratory Analysis

The baseline anti-NY-ESO-1 immune response and histologic and molecular changes in peripheral blood and tumor tissue and their association with clinical outcomes will be explored. In addition, a relationship between an induced anti-NY-ESO-1 immune response as well as tumor tissue changes during study treatment and clinical outcomes will be evaluated using peripheral blood and tumor tissue biopsies collected during study treatment at select sites.

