#### **5.1.3 Exploratory Efficacy Endpoint**

Intratumoral and peripheral blood anti-NY-ESO-1 immune changes biomarker analysis will be included in a Supplemental Statistical Analysis Plan (SSAP). This includes anti-NY-ESO-1 immune response and histologic and molecular changes in peripheral blood and tumor tissue and their association with clinical outcomes.

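### Protocol Table 3 lets a doubling of T-cell spot count be called induction even when both samples are ELISPOT-negative by the table's own cut-offs

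*Protocol*

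**What the plan says.** Protocol Section 6.3.2, Table 3, sets the ELISPOT positivity cut-offs in the row on T-cell immunity at baseline: "no less than 15 IFNγ-secreting spots per well after background subtraction" for the ex vivo assay and "no less than 50 spots per well after background subtraction" after in vitro stimulation. The same row states "The assay is performed in quadruplicate".

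A later row defines induction of T cells on treatment, at Day 92 and at Day 365 for subjects still free of progression. It gives two alternatives joined by *or*:

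- "Ratio of post-treatment to pre-treatment NY-ESO-1-specific T cell counts ≥ 2"
- "Post-treatment positive ELISPOT from pre-treatment negative baseline"

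The classification feeds Protocol Section 7.9, under which "a relationship between an induced anti-NY-ESO-1 immune response as well as tumor tissue changes during study treatment and clinical outcomes will be evaluated"; SAP Section 8.2.4 repeats this. SAP Section 5.1.3 defers the biomarker analysis to a supplemental SAP. For the laboratory side, Protocol Section 6.3.2 adds: "Details for sample handling and assay performance will be provided in the Laboratory Manual provided to study sites". Neither the supplemental SAP nor the Laboratory Manual is among the documents reviewed.

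**The concern.** The cut-offs of 15 and 50 enter the induction rule only through the conversion alternative. The ratio alternative has no minimum count, is not limited to baseline-positive subjects, does not say what to do when the background-subtracted baseline is zero or negative, and does not require the same assay format before and after. Nothing else in the protocol or SAP supplies these conditions.

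At low counts a doubling is easily produced by counting error, and it can happen in either arm. Such calls would raise the apparent placebo induction rate and place subjects without a real response in the induced group when induction is related to outcome. Protocol Section 1.1.2 describes induction as a pharmacodynamic marker and possibly a predictive one, so the label should mean what it says.

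**Working it through.** The plan states no error rate or sample size for this classification, so there is no figure of its own to reproduce.

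**1. The rule applied to example counts (spots per well, background subtracted).** *With floor* means that the ratio alternative also requires a positive post-treatment sample; conversion is kept.

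| Pre → post | Format (cut-off) | Both negative? | As written | With floor |
|---|---|---|---|---|
| 1 → 2 | ex vivo (15) | yes | induced | no |
| 2 → 4 | ex vivo (15) | yes | induced | no |
| 7 → 14 | ex vivo (15) | yes | induced | no |
| 24 → 48 | stimulated (50) | yes | induced | no |
| 0 → 2 | ex vivo (15) | yes | ratio undefined | no |
| 10 → 18 | ex vivo (15) | no | induced (conversion) | induced (conversion) |
| 20 → 40 | ex vivo (15) | no | induced (ratio) | induced (ratio) |

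As written, 1 → 2 qualifies and 0 → 2 does not.

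**2. How often chance alone meets the ratio alternative.** Assumptions, none of them from the documents except the four wells:

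- Spots per well are Poisson.
- Net count = mean of 4 antigen wells, Poisson(μ + b), minus mean of 4 control wells, Poisson(b).
- Pre and post are independent with the same μ, so there is no true change.
- False call = P(pre > 0, post ≥ 2 × pre, post negative).

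Hand check with b = 0 and μ = 0.5. The four-well total is Poisson(2), and the probability is Σ P(pre = k) × P(post ≥ 2k):

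- k = 1: 0.2707 × 0.5940 = 0.1608
- k = 2: 0.2707 × 0.1429 = 0.0387
- k = 3: 0.1804 × 0.0166 = 0.0030
- k = 4: 0.0902 × 0.0011 = 0.0001
- Sum ≈ 0.203, or about 20%

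Simulation of 1,000,000 subjects with b = 2, no extra between-sample variation (CV 0%) and the ex vivo cut-off:

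| True net spots per well | 0.5 | 1 | 2 | 3 | 5 | 7 | 10 |
|---|---|---|---|---|---|---|---|
| False call by ratio, post negative | 11% | 16% | 19% | 15% | 7% | 3% | 0.7% |

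Over b = 1 to 3 and between-sample CV of 0% or 30%, the range is about 5% to 20% for true counts of 0 to 5. At CV 0% it is 2%–4% at 7 spots and about 1% at 10. At CV 30% the decline is slower: the ratio alternative is still met in roughly 8%–10% at 10 spots. At CV 0% and true counts of 20 or more it is met in under 0.1%.

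**3. Effect of the floor.** At true counts of 0.5 to 5, false induction falls to about 0%. That is largely by construction, because those means lie far below 15. At a true mean of 14 with no change, about 22% are called induced both before and after the change, because those calls come through conversion.

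**4. What the floor does logically.** A negative baseline with a positive post-treatment sample is already a conversion. A baseline of at least 15 that doubles reaches at least 30 and is positive. So, within one assay format, the floored rule is the same as limiting the ratio alternative to baseline-positive subjects. A zero or negative baseline is a negative sample and is decided by conversion alone; no substitute count is needed.

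**5. Keeping conversion matters.** For a true ex vivo rise from 10 to 18 (b = 2, CV 0%), the rule as written detects 91%. The floor with conversion kept holds this at about 90%. A single rule requiring both positivity and doubling would cut it to 33%.

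**The case against.** The strongest reply is that the ratio alternative was meant for subjects with existing immunity and conversion for the rest. The antibody row has the same pairing (a fold rise, or seroconversion), and Protocol Section 1.1.2 separates increases from baseline from de novo responses. On that reading there is no low-count problem. The reading is plausible, but Table 3 does not state it, and an analyst applying the text literally would call 2 → 4 induced.

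Second, format matching, replicate handling and zero baselines may be settled in the supplemental SAP or Laboratory Manual. That may be so. Mixed formats, in particular, are only a possibility left open. But Table 3 already states the classification rule, so any floor set elsewhere should agree with it.

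Third, the simulated rates depend on where true counts lie. This stands in full: the documents give no count distribution, background or assay variability, and 0 to 5 spots is the region where the rule performs worst.

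A reader might infer that the induced-versus-not contrast in PFS or OS would shrink by 5% to 32%. Those figures come from 0.5/(0.5 + 0.5 × 0.05) = 0.95 and 0.3/(0.3 + 0.7 × 0.20) = 0.68. They assume that 30% to 50% of subjects are truly induced, that every other subject has a true count of 0 to 5, and that no true induction is missed. The documents support none of these. Nor can the frequency of an undefined ratio (up to 57% at a true net count of zero) be added to the false calls, since an undefined ratio does not meet the criterion.

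**Conclusion.** The gap is real on the text of Table 3: the ratio alternative can class as induced a subject who is ELISPOT-negative at both times, at Day 92 or Day 365. Under the illustrative Poisson model the false-call rate is about 5%–20% at true counts of 0 to 5 spots per well and, at CV 0%, 2%–4% at 7 and about 1% at 10. The actual rate in this trial cannot be derived from the documents.

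It would be wrong to read this as a threat to the trial's main conclusions. The classification is used only in exploratory analyses at select US sites, and Protocol Section 6.3.2 itself says that the predictive value of such tests is not yet known. PFS, OS, alpha, sample size and the secondary endpoints are untouched. Priority: minor.

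**What to change.** Amend the T-cell induction row of Table 3 and carry the same rule into the supplemental SAP, before unblinded immune data are seen. Induction is met by either:

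- a post-treatment sample that is positive by the Table 3 cut-off (15 ex vivo, 50 after stimulation) and at least 2-fold above the pre-treatment count in the same assay format; or
- a negative pre-treatment sample followed by a positive post-treatment sample.

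Report the continuous fold-change alongside.

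The cost is one table row and one sentence in the supplemental SAP, with no new samples or assays. There are two limits. A real rise that stays below the cut-off is no longer called induced, though it remains visible in the continuous summary. Chance conversion close to the cut-off is not cured.

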6.3.3 Tumor Biopsy

Biopsy samples will be collected as specified in the schedule of events ([Table 1](#), [Table 2](#)) and in accordance with the site's standard operating procedures. Details of biopsy collection are included in the Laboratory Manual.

6.3.4 ECOG

ECOG scores will be obtained according to the schedule of events ([Table 1](#), [Table 2](#)). The ECOG assessment tool is provided in [Appendix 2](#).

6.3.5 QoL Assessment

Quality of life will be assessed using a paper form completed by the subject according to the schedule of events ([Table 1](#), [Table 2](#)) using the EuroQol 5-Dimension 5 Level (EQ-5D-5L) for subject ≥ 18 years of age as shown in [Appendix 3](#). or using the EuroQol 5-Dimension Youth (EQ-5D-Y) for subjects 12 to < 18 years of age as shown in [Appendix 4](#).

6.4 Safety Assessments

The investigator is responsible for the appropriate medical care and safety of subjects who have entered this study. The investigator must notify the sponsor within 24 hours if any of the following events occurs:

- Any grade 3 or higher event, regardless of relationship to the study drug(s)
- Any event meeting the criteria for an SAE
- Any medical event of interest (MEOI) (see [Section 6.4.7.5](#))

Safety assessments will include solicited and unsolicited symptoms, physical examination findings, vital signs, documentation of AEs, ECGs and/or echocardiogram as applicable, clinical laboratory evaluations, deviations or discontinuations attributed to AEs, concomitant medication use, and LV305 persistence.

6.4.1 Physical Examination

A physical examination will be performed at Screening and should include an evaluation of organ systems, including, but not limited to, head and neck; chest and lungs; cardiac; gastrointestinal; neurologic; endocrine; and musculoskeletal and integument. Other organ systems should be evaluated as directed by medical history or current symptoms. At subsequent visits, limited, symptom-directed physical examinations should be performed.

Measurements of weight and height will be recorded only at screening and weight at every visit.

6.4.2 Vital Signs

Vital sign measurements will include systolic/diastolic blood pressure, respiratory rate, heart rate, and body temperature. On the day of each dosing, vital signs will be obtained before dosing and 30 minutes after dosing (± 10 -minute window). Blood pressure and heart rate will be measured no more than 60 minutes before the scheduled dosing. Vital signs should be performed before invasive procedures (e.g., blood sample collection).

6.4.3 Clinical Laboratory Tests

6.4.3.1 Laboratory Parameters

Central laboratory parameters to be analyzed are shown in [Table 4](#). Screening laboratory measurements will be used to determine study eligibility. Central laboratory measurements will be used for safety analyses and for other exploratory data analyses. Data on local laboratory tests may be collected for subjects experiencing adverse events upon sponsor notification. Sites will collect and analyze blood and urine samples at local laboratories based on their routine practice.

Table 4 Clinical Laboratory Tests (Central Laboratory)

Hematology	Hematocrit (Hct); hemoglobin (Hgb); mean corpuscular hemoglobin (MCH); mean corpuscular hemoglobin concentration (MCHC); mean corpuscular volume (MCV); platelet count; red blood cell (RBC) count; white blood cell (WBC) count with differential; absolute neutrophil count (ANC); absolute lymphocyte count
Serum Chemistry	Albumin; alkaline phosphatase; alanine aminotransferase (ALT); aspartate aminotransferase (AST); total protein; blood urea nitrogen (BUN); calcium; carbon dioxide; chloride; creatinine; creatinine clearance; uric acid; gamma-glutamyl transferase (GGT); glucose; lactate dehydrogenase (LDH); phosphorus; potassium; sodium; total bilirubin; direct bilirubin; thyroid stimulating hormone (TSH) (if TSH abnormal then T ₃ , T ₄ to be evaluated)
Coagulation	Prothrombin time (PT); partial thromboplastin time (PTT); international normalized ratio (INR)
Urinalysis	Appearance; bilirubin; color; glucose; ketones; microscopic examination of sediment; nitrite; occult blood; pH; protein; specific gravity; urobilinogen
Viral tests	Hepatitis B (HepB), hepatitis C (HepC), or human immunodeficiency virus (HIV) infection

